4.5 Exclusion Criteria

Patients presenting with any of the following will not be included in this study:

1. Drug-induced SLE, rather than “idiopathic” SLE.
2. Other systemic autoimmune disease (e.g., erosive arthritis, rheumatoid arthritis [RA], multiple sclerosis [MS], systemic sclerosis, or vasculitis not related to SLE).
 - a. RA-Lupus overlap (Rupus), and secondary Sjögren syndrome are allowed
3. Any major surgery within 6 weeks of study drug administration, (Day 0), or any elective surgery planned during the course of the study.
4. Any history or risk for tuberculosis (TB), specifically those with:
 - a. Current clinical, radiographic, or laboratory evidence of active TB
 - b. History of active TB
 - c. Latent TB defined as positive QuantiFERON-TB Gold In-Tube (QFT-G) or other diagnostic test in the absence of clinical manifestations. Latent TB is not excluded if the patient has documented completion of adequate course of prophylactic treatment with regimen recommended by local health authority guideline, or the patient has started treatment with isoniazid, or other regimen recommended by local health authority guidelines for at least 1 month before Day 0 and continues to receive the prophylactic treatment during study until the treatment course is completed.
5. Active or unstable lupus neuropsychiatric manifestations, including but not limited to any condition defined by BILAG A criteria, with the exception of mononeuritis multiplex and polyneuropathy, which are allowed.
6. Severe proliferative lupus nephritis, (WHO Class III, IV), which requires or may require induction treatment with cytotoxic agents or high dose CS.
7. Concomitant illness that, in the opinion of the Investigator or the sponsor or their designee, is likely to require additional systemic glucocorticosteroid therapy during the study, (e.g., asthma), is exclusionary.
 - a. However, treatment for asthma with inhalational CS therapy is allowed.

8. Use or planned use of concomitant medication outside of standard of baseline treatment for SLE from Day -1 or for any time during the study. (See [Section 4.6.2](#) for prohibited concomitant medication).
9. Active and clinically significant infection (bacterial, fungal, viral, or other) within 60 days prior to first dose of study drug. Clinically significant is defined as requiring systemic parenteral antibiotics or hospitalization.
10. A history of opportunistic infection, or a history of recurrent or severe disseminated herpes zoster or disseminated herpes simplex within the last 3 years.
11. Chronic viral hepatitis including hepatitis B (HBV) and hepatitis C (HCV) unless patient received curative treatment for HCV and has a documented negative viral load, known human immunodeficiency virus (HIV), or acquired immunodeficiency syndrome (AIDS)-related illness.
12. Cryptosporidium in the stool sample at screening.
13. White blood cells (WBC) $< 1,200/\text{mm}^3$ ($1.2 \times 10^9/\text{L}$) at screening.
14. Absolute neutrophil count (ANC) $< 500/\text{mm}^3$ at screening.
15. CD4+ count $< 150/\mu\text{L}$ at screening.
16. Platelets $< 50,000/\text{mm}^3$ ($50 \times 10^9/\text{L}$) or $< 35,000/\text{mm}^3$ ($35 \times 10^9/\text{L}$) if related to SLE, at screening.
17. Hemoglobin $< 8 \text{ g/dL}$ or $< 7 \text{ g/dL}$ at screening if related to SLE.
18. Proteinuria $> 3.0 \text{ g/day}$ (3000 mg/day) at screening or equivalent level of proteinuria as assessed by protein/creatinine ratio (3 mg/mg or 339 mg/mmol).
19. Serum creatinine $> 2.0 \text{ mg/dL}$ at screening or creatinine clearance (CrCL) $< 40 \text{ mL/minute}$ based on Cockcroft-Gault calculation³⁹:
$$\text{GFR} = ([1 \text{ for male}] \text{ or } [0.85 \text{ for female}]) \times (140 - \text{Age}) \times \text{BW}/(72 \times \text{Creatinine}).$$
20. Serum ALT and/or serum AST $> 2 \times \text{ULN}$ at screening, unless explicitly related to lupus based on the Investigator's judgment.
21. Creatinine kinase (CK) $> 3.0 \times \text{ULN}$ at screening, unless it is related to lupus myositis.
22. Total bilirubin $> 1.5 \times \text{ULN}$ at screening (unless related to Gilbert's syndrome).
23. Any other laboratory test results that, in the opinion of the Investigator or the sponsor or sponsor's designee, might place a patient at unacceptable risk for participating in this study.

24. History of allergic or anaphylactic reaction to any therapeutic or diagnostic monoclonal antibody (e.g., IgG protein) or molecules made of components of monoclonal antibodies.
25. History substance and/or alcohol abuse or dependence within the past 1 year, at the Investigator's judgment.
26. History of cancer within the last 5 years (except for cutaneous basal cell or squamous cell cancer, or cervical cancer *in situ* resolved by excision).
27. Any other severe acute or chronic medical or psychiatric condition, including recent (within the past year) medical conditions (e.g., cardiovascular conditions, respiratory illnesses) that may increase the risk associated with study participation or investigational product administration or may interfere with the interpretation of study results and, in the judgment of the Investigator, sponsor or sponsor's designee, would make the patient inappropriate for entry into this study.
28. Investigational site staff members directly involved in the conduct of the trial and their family members, site staff members otherwise supervised by the Investigator, or patients who are employees of the sponsor or directly involved in the conduct of the trial.
29. Currently participating in, or who have participated in other interventional (drug or device) clinical study within 30 days or 5 half-lives of baseline, whichever is longer.
30. Recent (within the past 12 months) or active suicidal ideation or behavior based on patient responding "yes" to question 3, 4 or 5 on the C-SSRS.
31. Current or pending incarceration.
32. Current or pending compulsory detainment for treatment of either a psychiatric or physical (e.g., infectious disease) illness.
33. Currently taking a total daily dose of > 30 mg morphine or morphine equivalent (see [Appendix 7](#)).
34. Body mass index (BMI) \geq 40.0.

4.6 Concomitant Medications

Any medicinal product, prescribed or OTC, including herbal and other nontraditional remedies, is considered a concomitant medication. Patients should stay on stable regimen (not PRN) of other concomitant medications for the treatment of SLE (e.g., analgesics, nonsteroidal anti-inflammatory drugs [NSAIDs], statins, ACE inhibitors/ARBs and other antihypertensive drugs), unless changes in these treatments are clinically indicated. Patients should refrain from Tylenol, NSAIDs, and any pain medications including tramadol and other opiates for at least 12 hours before each visit, with the exception of the Screening Visit.

Use of any other drugs for non-SLE conditions, including over-the-counter medications and herbal preparations, should remain stable unless change or addition is clinically necessary. Discussion with the medical monitor prior to initiation of new medication is strongly recommended. Any concomitant therapies must be recorded on the eCRF. Prior and concomitant medication use will be recorded for the 30 days prior to screening until the last follow-up visit. In addition, historical treatment for SLE (including immunosuppressant, anti-malarial, corticosteroid, and/or biologic agent including investigational agents) will be recorded for the 48 weeks prior to screening in the eCRF.

4.6.1 Corticosteroid

Prior to randomization, oral CSs (prednisone or prednisone equivalent), may be used in accordance with the Investigator's clinical judgment and best standard of care. See [Appendix 3](#) for examples of equivalents.

- A maximum daily dose of 30 mg/day of oral CS will be acceptable for eligibility for the study. For patients whose only SLE treatment is steroids, their stable steroid dose must be at least 10 mg/day and no more than 30 mg/day for a minimum of 6 weeks at time of randomization on Day 0
- Topical steroids may be used, but the dose must be stable for at least 6 weeks prior to Day 0, and be maintained at a constant dose throughout the study duration until the rashes resolve. PRN topical steroids are not permitted
- Once the patient has received the first dose of study drug (Day 0), tapering of oral steroids will be highly encouraged and should be continually evaluated during the protocol-allowed tapering windows (Day 0 through Day 150) with the target of achieving a CS daily dose of < 7.5 mg and < Day 0 dose between Day 150 and Day 210
- Between Day 150 and Day 210 (i.e., within 60 days of primary endpoint assessments), oral CS doses must be held constant
- CS Burst for SLE-related Indications

After Day 0 (first dose of study drug), a maximum of 1 oral CS "burst" equivalent to ≤ 40 mg/day prednisone for increased SLE disease activity will be allowed between Day 0 and Day 120, which must be tapered down to the baseline (Day 0) CS dose or lower within 14 days of initiation of the "burst". Any "burst" continuing after Day 120 or occurring after Day 120 is considered a protocol deviation.

- Alternatively, a single intramuscular (IM) dose of methylprednisolone (< 40 mg) is permitted during this period

CS Burst for Non-SLE-related Indications.

A single treatment of oral prednisone equivalent of ≤ 40 mg/day for 14 days is permitted for a non-SLE indication, though it must be completed prior to Day 120. No long acting steroid injections are permitted.

Note: Treatment with inhaled CS are allowed for the treatment of non-SLE-related indications only (e.g., for asthma).

Any other increase from baseline of CS dose or systemic use of CS of any kind (including intra-articular and intravenous administration) are not permitted from Day 0 through Day 210 and will result in the patient being considered a treatment failure. There is no restriction of CS usage after Day 210.

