2.2 Phase 2 Proof of Concept

OBJECTIVES	ENDPOINTS
Primary	

 • To demonstrate a superior effect of BOS161721 at the chosen dose compared with placebo for response on the SRI-4 	Primary Efficacy Endpoint 
 • The proportion of patients with a SRI-4 response at Day 210 (see Section 6.3.4.1)
Secondary	

 • To demonstrate a superior effect of BOS161721 at the chosen dose compared with placebo for response on clinical indicators of SLE activity, in adult patients with moderately to severely active SLE on limited background standard of care treatment 	Secondary Efficacy Endpoints 
 • The proportion of patients with: 
 - SRI-4 response at each visit - SRI-5 and SRI-6 response at each visit (Section 6.3.4.2) - a sustained reduction from baseline of oral corticosteroid (CS) (≤ 7.5 mg/day and $<$ Day 0 dose) between Day 150 and Day 210 - new or recurrent BILAG flares (≥ 1 qualifying BILAG A or > 1 qualifying BILAG B) through Day 210 - PGA worsening - a BICLA response - a CLASI response

	
 - medication failures • The changes and percent changes from baseline in: 
 - CLASI - PGA - Total number of swollen joints, tender joints, and active joints (swelling and tenderness in the same joint) in the ACR-28 joint count - SLEDAI-2K - SLICC/ACR damage index • Time to medication failure • Group mean percent reduction in CS administration from baseline Day 0 dose through Day 210 in patients receiving ≥ 7.5 mg/day prednisone equivalent at Day 0 • Duration of longest SRI-4 response • Time to first BILAG flare (≥ 1 new or recurrent BILAG A or > 1 new or recurrent BILAG B) relative to baseline through Day 210
--	--

Safety

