4.6.2 Other Prohibited and/or Restricted Treatments

Prohibited and/or restricted medications taken prior to study drug administration and during the study are described below, and washout requirements are provided in [Appendix 4](#). All medications taken within 30 days prior to screening must be recorded on the eCRF.

1. Prior exposure to BOS161721
2. Patients who have received treatment with anti-CD20 monoclonal antibodies within 24 weeks of screening
3. Patients who have received treatment with cyclophosphamide within the 24 weeks prior to screening
4. Patients who have received treatment with cyclosporine (with exception of ophthalmic use), any other calcineurin inhibitor or other immunosuppressive medication not specified in the inclusion criteria within 4 weeks for oral use or 8 weeks for topical use of screening
5. Patients who are currently receiving or are scheduled to receive plasmapheresis or lymphapheresis therapy, or have received such therapy within 24 weeks prior to screening
6. Patients who have received any live vaccines within 30 days of screening. Note: Furthermore, live vaccines should not be used during the course of the study and within the 2 months following last dose. Other inactivated vaccines such as tetanus, etc., may be used according to local guidelines during treatment period
7. Patients who are scheduled or anticipated to have elective surgery during the course of the study
8. Initiation of new immunosuppressant or anti-malarial agent is not permitted. Note: Dose reduction or replacement may be allowed due to intolerability or shortage for patients on a stable dose prior to study initiation

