5.4 Safety Follow-Up Visits

Safety follow-up visits will take place at Days 210, 240, and 270. These visits will include the following assessments as indicated in the Schedule of Assessments (Table 1 and Table 4):

- PROs: CCI [REDACTED]
- Documentation of AEs and SAEs (see Section 6.2.2.5 on SAE reporting requirements)
- Injection site reactions
- Targeted physical examination
- Vital signs (prior to PK blood draw)
- Spot urine for protein/creatinine ratio and urinalysis
- Concomitant medication documentation
- BILAG-2004 Index, SLEDAI-2K, ACR-28 joint count, CLASI, and PGA
- Fasting clinical laboratory assessments (hematology and clinical chemistry)
- Direct Coomb's test (if indicated for hemolytic anemia)
- Plasma CCI [REDACTED]
- CCI [REDACTED]
- 12-lead ECG (prior to PK blood draw)
- CRP
- ADA
- CCI [REDACTED]
- Urine pregnancy test
- See Table 1 and Table 4 for details of PK sampling in the MAD and POC portions, respectively

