6.3.1 SLEDAI-2K

The SLEDAI-2K is a validated instrument that measures disease activity in SLE patients at the time of the visit and in the previous 30 days. It is a global index and includes 24 clinical and laboratory variables that are weighted by the type of manifestation, but

not by severity. The total score falls between 0 and 105, with higher scores representing increased disease activity. The SLEDAI-2K has been shown to be a valid and reliable disease activity measure in multiple patient groups. A SLEDAI -2K of 6 or more generally represents moderately to severely active disease.⁴⁴

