6.3.4.3 BICLA Response

The BICLA is a responder index developed to measure response to therapy, and it includes scores from the BILAG, SLEDAI-2K, and PGA. BICLA response is defined as: 1) at least 1 gradation of improvement in baseline BILAG 2004 scores in all body systems with moderate disease activity at entry (e.g., all B [moderate disease] scores falling to C [mild], or D [no activity]); 2) no new BILAG A or more than 1 new BILAG B scores; 3) no worsening of total SLEDAI-2K score from baseline; 4) $\leq 10\%$ deterioration in PGA score; and 5) no treatment failure.⁴⁴ It is driven primarily by the BILAG, and has been used in phase 2 and 3 mAb studies.⁴⁷

For the endpoints of BICLA response at Days 210, 240, and 270, patient scores will be completed and response determined.

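### The steroid treatment-failure rule stops at Day 210, but BICLA, which requires no treatment failure, is also set at Days 240 and 270, so a patient first given more steroids after Day 210 can count as a responder

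*Protocol*

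**What the plan says.** All references are to the current protocol (V7.0, Amendment 6). The SAP was not available.

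- **Steroid rule (4.6.1).** Apart from the permitted bursts, increases over the baseline dose and other systemic use "are not permitted from Day 0 through Day 210 and will result in the patient being considered a treatment failure". The section then adds: "There is no restriction of CS usage after Day 210".
- **Other rescue (4.6.2, item 8).** "Initiation of new immunosuppressant or anti-malarial agent is not permitted". No end day is given.
- **BICLA (6.3.4.3).** The fifth component is "5) no treatment failure". On timing: "For the endpoints of BICLA response at Days 210, 240, and 270, patient scores will be completed and response determined".
- **SRI (2.2, 6.3.4.1, 6.3.4.2).** The secondary endpoints include "SRI-4 response at each visit", with the same timing for SRI-5 and SRI-6. The SRI definitions have no medication component.
- **Visits (5.4).** "Safety follow-up visits will take place at Days 210, 240, and 270". SLEDAI-2K, BILAG and PGA are collected at all three.
- **Analysis rule (8.2.3, 8.2.4).** Prohibited medication, or steroid use unallowable under Section 4.6, makes a patient a non-responder from that date. The sentence is limited to the primary efficacy analysis. Secondary and exploratory endpoints are to be judged on the same statistical hypothesis. Handling of medication failures in secondary endpoints is left to the SAP.

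**The concern.** BICLA and the steroid rule use the same term, treatment failure, but over different periods. The endpoint runs to Day 270 and the rule stops at Day 210. Within those last 60 days, a new immunosuppressant is still prohibited while steroids of any dose are not.

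A patient with active disease at Day 210 who is then brought under control with steroids could therefore be scored a BICLA responder at follow-up. The between-arm comparison at that visit would mix the effect of study drug with the effect of free steroid use.

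The later days do not look accidental. Where a Day 210 limit was wanted, the protocol wrote one: for BILAG flares, for both steroid-reduction endpoints and, in Section 6.3.5, for CLASI response.

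**Working it through.** **1. The plan's own figure.** Section 8.1 gives 96 evaluable patients for 62% vs 33% at Day 210, 2:1 allocation, two-sided 10%, 80% power. Let d = 0.29 and p̄ = (0.33 + 2×0.62)/3 = 0.5233.

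- Uncorrected placebo n = [1.645·√(1.5·p̄(1−p̄)) + 0.842·√(0.33×0.67 + 0.62×0.38/2)]² / d² = [1.006 + 0.490]² / 0.0841 = 26.6. This rounds to 27, a total of 81.
- With continuity correction, n′ = (26.6/4)·[1 + √(1 + 3/(26.6×0.29))]² = 31.6. This rounds to 32, a total of 96.

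The stated N reproduces with the continuity-corrected formula. It depends on Day 210 only, so nothing below changes it.

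**2. Which visits the rule misses.** Efficacy is scored after baseline at Days 30, 60, 90, 120, 150, 180, 210, 240 and 270. Two of these nine visits fall after the steroid rule ends.

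**3. Why mainly Day 270.** SLEDAI-2K scores activity "at the time of the visit and in the previous 30 days" (6.3.1). BILAG scores the last 4 weeks (6.3.2).

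| Visit | SLEDAI-2K window opens | BILAG window opens |
|---|---|---|
| Day 240 | 240 − 30 = Day 210 | 240 − 28 = Day 212 |
| Day 270 | 270 − 30 = Day 240 | 270 − 28 = Day 242 |

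At Day 240, a flare that led to steroids just after Day 210 is usually still inside the window. At Day 270, steroids started on Day 211 have been running for 240 − 211 = 29 days (SLEDAI-2K) or 242 − 211 = 31 days (BILAG) before the window opens. Visit windows of ±3 days shift these figures slightly.

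**4. Scale.** 96 at 2:1 is 64 active and 32 placebo.

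- One converted placebo patient: 1/32 = 3.1 points, lowering the difference.
- One converted active patient: 1/64 = 1.6 points, raising it.

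**5. Illustration of direction.** The protocol gives no BICLA rates and no rate of steroid use after Day 210. Assume, for illustration only, that the SRI-4 planning rates hold at Day 270 and that shares kA and kP of the active and placebo non-responders convert, each between 5% and 20%:

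Difference = (62 + 38·kA) − (33 + 67·kP)

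| kA | kP | Active | Placebo | Difference |
|---|---|---|---|---|
| 0.05 | 0.05 | 63.9 | 36.35 | 27.55 |
| 0.20 | 0.20 | 69.6 | 46.4 | 23.2 |
| 0.05 | 0.20 | 63.9 | 46.4 | 17.5 |
| 0.20 | 0.05 | 69.6 | 36.35 | 33.25 |

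A different model gives a different answer. If 5% of all patients in each arm are rescued and a share s of them is scored as responders, the difference is (62 + 5s) − (33 + 5s) = 29, unchanged. The direction therefore depends on the model and on the unknown rates.

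**The case against.** **The SAP may settle it.** Section 8.2.4 sends medication-failure handling in secondary endpoints to the SAP, and the non-responder rule in 8.2.3 is confined to the primary analysis. This stands for SRI-4/5/6, whose definitions contain no failure component. A reader might infer that the protocol already lets steroid-rescued patients count as SRI responders at Day 270. It does not say so. That follows only if the SAP adopts the Section 4.6 definition without extending it. BICLA is different: its failure component is in the protocol, and the only passage giving treatment failure a meaning for steroids stops at Day 210.

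**BICLA's status at the later days is unclear.** The secondary list in 2.2 names BICLA without a day, and the exploratory list is redacted. This matters little, because 8.2.3 applies the same hypothesis to secondary and exploratory endpoints.

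**The release of steroids is deliberate.** The last dose is at Day 180, the later visits are labelled safety follow-up, and response regardless of later steroids is a legitimate estimand. All of this stands, and freeing steroids for care is not a fault. But a composite that names treatment failure as a component is not a regardless-of-steroids measure. The protocol should say which is meant after Day 210.

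**The numbers prove no harm.** Correct. A reader might infer that the bias dilutes the drug effect, or that the roughly 24 active (64×0.38) and 21 placebo (32×0.67) Day 210 non-responders cap the number who could convert. Neither is supported. Some of those patients may already be medication failures and stay non-responders, while Day 210 responders held in response by later steroids would be additional.

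**Conclusion.** The point holds for BICLA at Days 240 and 270, with the practical exposure mainly at Day 270. It holds for SRI-4, SRI-5 and SRI-6 at those visits only if the SAP carries over the Section 4.6 definition unchanged. It assumes that treatment failure in 6.3.4.3 means what 4.6.1 says it means; no other meaning is given.

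The size and direction of any bias cannot be determined from the protocol. The per-patient figures of 3.1 and 1.6 points give a scale, and the illustrative differences of 17.5 to 33.25 points rest on assumed conversion shares.

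A reader might infer that the trial's main conclusion is at risk. It is not: superiority is judged on SRI-4 at Day 210, inside the rule, and the endpoints limited to Day 210 are also untouched. Severity is minor.

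**What to change.** Keep steroids unrestricted for clinical care after Day 210. Limit between-arm tests of BICLA and SRI-4/5/6 to visits through Day 210, and present Days 240 and 270 descriptively.

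If those days are to be tested, state before unblinding that a systemic steroid increase for SLE above the Day 0 dose after Day 210 counts as treatment failure from that date. The Day 0 reference matches 4.6.1 and does not penalise a patient who tapered successfully. A sensitivity analysis can use the Day 210 dose instead. Leave the primary analysis as it is.

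The cost is wording in the protocol or SAP. Section 4.6 already has concomitant medication recorded to the last follow-up visit, so no new data are needed. The downside is fewer tested follow-up time points or, under the second option, lower stated response rates at follow-up.
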